# 18.0 Glossary of Abbreviations

Glossary of Abbrevia	ations:
AD	Alzheimer's Disease
AE	Adverse event
ATC	Anatomic Therapeutic Chemical
AUC 0-t	Area under the plasma concentration-time curve, from time 0 to time t
AUC 0-last	Area under the curve from the time of dosing to the time of the last measurable (positive) concentration
BLQ	Below the Limit of Quantification
CI	Confidence Interval
CV	Coefficient of Variation
C max	Maximum observed concentration.
COVID-19	Coronavirus Disease 2019
CRF	Case Report Form
CSR	Clinical Study Report
ECG	Electrocardiogram
eCRF	Electronic Case Report Form
IP	Investigational Product
LLOQ	Lower Limit of Quantification
MedDRA	Medical Dictionary for Regulatory Activities
PCS	Potentially Clinically Significant
PT	MedDRA Preferred Term
Q1	First Quartile
Q3	Third Quartile
SAP	Statistical Analysis Plan
SAE	Serious Treatment-emergent Adverse Event
SI	International System of Units
SOC	MedDRA System Organ Class
Std	Standard Deviation
TEAE	Treatment Emergent Adverse Event
WHO	World health Organization

## 19.0 Appendix

## 19.1 Appendix-A Schedule of Study Assessment

Study Period	Screening	Base	eline		Trea	tment		Follo	w Up
Study Day	D -21 to D -8	D -7 (±1 d)	D -1	D 1	D 4 a			D 21 a (±1 d)	
Informed consent b	X								
Inclusion/exclusion criteria	X	X	X						
Medical history and demographics c	X								
Body weight	X			X		X	X		X
Body height	X								
CDR	X								
Test of Premorbid Functioning	X								
Vital signs d	X	X	X	X		X	X		X
Physical examination e	X	X	X				X		
EEG f	X								
12-lead ECG g	X		X	X		X	X		X
C-SSRS h	X	X	X	X		X	X		X
Clinical laboratory tests i	X		X			X	X		X
Alcohol test j	X	X							
Urine drug test	X	X	X	X		X	X		
FSH test k	X								
Pregnancy test 1	X		X				X		X
Serology test m	X								
MRI n	X								
Study Period	Screening	Base	eline		Trea	tment		Follow	Up

Study Day	D -21 to D -8	D -7 (±1 d)	D -1	D 1	D 4 a		D 14 or ET	D 21 a (±1 d)	
Participant training p, q		X	X						
Pamata assassments V									
Remote assessments v					X (ana	- d-:1)			
IP self-administration w					X (one	e daily)	)		
IP dispensation x IP accountability y				X	2	X			
Safety telephone call					X			X	
TEAEs/SAEs					X				
Concomitant medications z					X				

Abbreviations: CDR = Clinical Dementia Rating Dementia Staging Instrument®; C-SSRS = Columbia—Suicide Severity Rating Scale; d = days; ECG = electrocardiogram; EEG = electrocarcephalogram; ET = early termination; FSH = follicle stimulating hormone; HIV = human immunodeficiency virus; IP = investigational product; MRI = magnetic resonance imaging; PET = positron emission tomography; SAE = serious adverse event; TEAE = treatment-emergent adverse event

Notes: In the event of ET, efforts should be made to collect the Day 14 visit assessments.

When scheduled for the same time point, procedures should be performed in the following order: vital signs, ECG, blood draws, morning meal, IP dosing, then any scheduled postdose assessments.

In the setting of public health advisories due to COVID-19, assessments scheduled to be conducted at the study site may be performed via telephone/video if feasible. For assessments that cannot be conducted by phone or video, an in-home visit may be conducted. Information about COVID-19 diagnosis, treatment, and quarantine status will be collected with the medical history, AEs, and prior and concomitant medications.

a Day 4 and Day 21 visits will occur via scheduled telephone calls.

Protocol no: 718-CNA-201 b Both study partners and participants are to be consented during the Screening Period. c In addition to full medical history, all nonpharmacological methods (eg. used to treat or prevent of AD are to be recorded. d Vital signs to include temperature, respiratory rate, heart rate, and blood pressure. Heart rate and blood pressure to be collected in supine position and standing position at all scheduled time points. When scheduled for the same visit, vital signs are to be assessed prior to ECG and blood collection. e Full physical examination to be conducted at Screening, abbreviated examinations thereafter. Unscheduled, symptom-directed physical examinations may also be conducted at the investigator's f EEG to be performed for all participants during Screening. If clinical events suspicious for seizure occur, an unscheduled 1-hour EEG will be performed (with a second follow-up 1-hour EEG at the discretion of the investigator). g ECG will be measured after the participant has been in the supine position for at least 5 minutes. h "Baseline/Screening" C-SSRS form at Screening and "Since Last Visit" C-SSRS form thereafter. i Samples for clinical laboratory assessments for hematology, biochemistry, coagulation, urinalysis, and serology to be collected ≤2 hours prior to dosing during the Treatment Period, and any time of day at other time points. Participants are to be in a fasted state for screening assessments only. j Alcohol testing will be performed in the clinic, either by urine dipstick or breathalyzer. k To confirm self-reported postmenopausal status in women only. I Serum pregnancy tests for all female participants at Screening; urine pregnancy tests will be conducted for all female participants who are not postmenopausal or surgically sterile at other scheduled time points. m To include testing for hepatitis B and C, HIV-1, and HIV-2 n Only in participants without an MRI report obtained within the 2 years preceding the Baseline Period p Where participant informed consent is given, samples for exploratory biochemical research and genetic testing will be collected after the collection of samples, according to the schedule in Table 3. q Participants and study partners will be trained to use all study-related software and devices. Additional guidance will be provided on choosing a meal with approximately 30 g of fat.

v Daily reminders will be sent to participants to complete assessments of

or in the clinic during the

Treatment Period (with observation by study staff during scheduled clinic visits).

- w On visit days during the Treatment Period, participants will self-administer IP in the clinic under the supervision of study staff after the predose assessments and consumption of a morning meal.
- x Study staff will dispense sufficient IP for daily dosing at home until the next scheduled visit. On Days 7 and 14, participants will return used IP packaging and any unused IP for site staff to document.
- y On Days 7 and 14, participants will return used IP packaging and any unused IP for site staff to document.
- z At Screening, include all psychotropic medications used within 12 weeks of informed consent, any other medications and supplements taken within 60 days of informed consent, and all medication used to treat AD, regardless of timing. After Screening, all changes to any medication or supplements should be captured.

## 19.2 Appendix-B Prior and Concomitant Medication Start/Stop Date Imputation

Imputation Rules for Partial Dates (D = day, M = month, Y = year)

Parameter	Missing	Additional Conditions	Imputation
Start date for con meds	D only	M and Y same as M and Y of investigational product administration	Date of investigational product administration
		M and/or Y not same as date investigational product administration	First day of month
	M and D	Y same as Y of investigational product administration	Date of investigational product administration
		Y not same as Y of investigational product administration	Use Jan 01 of Y
	M, D, and Y	None - date completely missing	Day prior to date investigational product administration
Stop date for con meds	D only	M and Y same as M and Y of investigational product administration	Date of investigational product administration
		M and/or Y not same as date of investigational product administration	Last day of month
	M and D	Y same as Y of investigational product administration	Date of investigational product administration
		Y not same as Y of investigational product administration	Use Dec 31
	M, D, and Y	None - date completely missing and NOT ongoing	Date of investigational product administration

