13.6.6. Prior and Concomitant Medications

Medications will be recorded at each study visit during the study and will be coded using World Health Organization-Drug dictionary September 2015, or later.

At Screening, all psychotropic medications used by the participant within 12 weeks before informed consent, any other medications and supplements within 60 days before informed consent, and all medications used to treat AD, regardless of timing, will be recorded. After Screening, all changes to any medication or supplements should be captured. Those medications taken prior to the first dose of IP will be denoted "Prior". Those medications taken prior to the first dose of IP and continuing beyond the initiation of the IP or those medications started at the same time or after the initiation of the IP will be denoted "Concomitant".

Medications will be presented according to whether they are "Prior" or "Concomitant" as defined above. If medication dates are incomplete and it is not clear whether the medication was concomitant, it will be assumed to be concomitant.

Details of prior and concomitant medications will be listed by participant, start date, and verbatim term.

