#### 13.8 Prior and Concomitant Medications

The following analyses will use the Safety Set

All medications taken and procedures undergone during the study will be recorded.

Medications will be presented according to whether they are being taken prior to and/or during the study (concomitant). Prior medications are defined as those taken prior to the initiation of the start of the investigational product, and that ended prior to the IP. Concomitant medications are defined as those with a start date on or after the first dose of investigational product or those with a start date before the first dose of investigational product that is ongoing or with a stop date on or after the first dose of investigational product.

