### 19.3 Appendix-C Adverse Event Start/Stop Date Imputation

Parameter	Missing	Additional Conditions	Imputation
Start date for AEs	D	M and Y same as M and Y of investigational product administration	Date of investigational product administration
		M and/or Y not same as date investigational product administration	First day of month
	D and M	Y same as Y of investigational product administration	Date of investigational product administration
		Y prior to Y of investigational product administration but same as Y of screening date	Date of screening date
	D, M, Y	None - date completely missing	Date of investigational product
Stop date for AEs	D	M and Y same as M and Y of investigational product administration	Date of investigational product administration
		M and/or Y not same as date of investigational product administration	Use last day of month
	D and M	Y same as Y of investigational product administration	Date of investigational product
		Y not same as Y of investigational product administration	Use Dec 31
	D, M, Y	None - date completely missing	No imputation, but assume ongoing

[figure not shown]
Note: In all cases, if an estimated start date is after a complete stop date, use the first day of the stop date month. Similarly, if the estimated stop date is before a complete or imputed start date, use the last day of the start day month.

[figure not shown]

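### Appendix B can give a medication that is known to have ended before dosing a start date on the dosing day, so it falls under both the prior and the concomitant definitions

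*SAP*

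**What the plan says.** SAP Appendix B (19.2) has five rows for incomplete medication start dates. Two of them set the start to the date of dosing:

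- day missing, with the condition "M and Y same as M and Y of investigational product administration" (the same words also head a stop-date row; the start-date row is meant here);
- month and day missing, with the condition "Y same as Y of investigational product administration".

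A completely missing start becomes "Day prior to date investigational product administration". The other two rows use the first day of the recorded month or 1 January of the recorded year. No row refers to the stop date, and no note follows the table.

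SAP 13.8 sorts medications into two classes. "Concomitant medications are defined as those with a start date on or after the first dose of investigational product"; a second limb covers earlier starts that are ongoing or that stop on or after the first dose. Prior medications are those taken before the IP "and that ended prior to the IP".

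SAP Appendix C (19.3), for adverse events, carries a repair note: "In all cases, if an estimated start date is after a complete stop date, use the first day of the stop date month". It then gives the mirror rule for an imputed stop that precedes the start. SAP 13.1 assigns Appendix B to medications and Appendix C to adverse events.

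Protocol 13.6.6 sets the default: "If medication dates are incomplete and it is not clear whether the medication was concomitant, it will be assumed to be concomitant". SAP 6.1, which lists changes from the protocol, records no change to this rule.

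**The concern.** The first limb of the concomitant definition needs only a start date on or after the first dose. Under the two rows above, the imputed start always satisfies it, whatever the recorded stop date. A drug recorded as stopped weeks before dosing can thus become eligible for the concomitant table, with a start later than its stop.

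The protocol's default does not justify this, because it applies where the status is unclear, and a complete stop date before dosing makes it clear.

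At stake are the prior and concomitant medication tables (14.1.3 and 14.1.4) and the medication listing. The protocol records all medication for AD whatever its timing (9.2.1). It excludes memantine only within the four weeks before IP (8.2), but prohibits it on study (9.2.2). A participant who stopped memantine in time could be shown as taking a prohibited drug on study.

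**Working it through.** The plan gives no figure to reproduce. The check applies the written rules to dates.

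**Inputs.** Start-date rows from SAP Appendix B; class definitions from SAP 13.8; repair note from SAP Appendix C. Assumption: first dose on 20 May 2021, chosen only for illustration.

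**Rule applied.** Concomitant by start if the imputed start is on or after 20 May 2021. Ended before dosing if the recorded stop is before 20 May 2021.

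| Recorded start | Recorded stop | Appendix B start | Start relative to stop | Concomitant by start | Ended before dosing |
|---|---|---|---|---|---|
| May 2021, day missing | 10 May 2021 | 20 May 2021 | 10 days after | yes | yes |
| 2021, month and day missing | 1 Mar 2021 | 20 May 2021 | 80 days after | yes | yes |
| completely missing | 1 Mar 2021 | 19 May 2021 | 79 days after | no | yes |
| Feb 2021, day missing | 1 Mar 2021 | 1 Feb 2021 | before | no | yes |
| 2020, month and day missing | 1 Mar 2021 | 1 Jan 2020 | before | no | yes |

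(1 March to 20 May is 30 + 30 + 20 = 80 days.)

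The first two lines meet both definitions, and SAP 13.8 has no tie-break. The third has impossible dates but is not made concomitant. The last two behave properly.

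**Every case under the two rows.** Take all true start/stop pairs that end before 20 May 2021.

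- Day missing, dosing month: 19 possible days (1 to 19 May), so 19 × 20 / 2 = 190 pairs. All 190 meet the concomitant definition by start.
- Month and day missing, dosing year: 31 + 28 + 31 + 30 + 19 = 139 possible days, so 139 × 140 / 2 = 9,730 pairs. All 9,730 meet it.

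These totals are 100% by construction, because the imputed start is always the dosing date. They show that the rule has no exception, not that such records are common.

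**With the Appendix C note applied to medications.** The start moves to the first day of the stop month: 1 May 2021 in the first line and 1 March 2021 in the second. That day cannot be later than the stop, which precedes dosing. The counts become 0 of 190 and 0 of 9,730.

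**Mirror case.** A start of 25 May 2021 with a stop of May 2021, day missing, gets an imputed stop of 20 May 2021, five days before the start. The class is unaffected, since the start is after dosing, but the listed dates are impossible and Appendix B does not repair them.

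**The case against.** The strongest objection is that SAP 13.8 also defines prior medications by their end. A drug with a complete stop before dosing satisfies that condition whatever its imputed start. The SAP is to be read with the protocol (SAP 6.0), and protocol 13.6.6 points to prior when the status is clear. A careful programmer could therefore classify the record correctly. This stands: a reader might infer that the tables will be wrong, and the documents support only that they could be. It does not remove the conflict, because the concomitant limb is equally explicit.

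Second, the affected set is narrow. A record needs a partial start in the dosing month or year together with a complete stop before dosing. AD drugs begun in earlier years are imputed to 1 January of their year and classified properly. In the day-missing row, start and stop both fall in the dosing month, mostly inside the four-week stability window of inclusion criterion 10b. It is tempting to call year-only start dates likely because AD drugs are recorded regardless of timing; no figure in the documents supports that.

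Third, one might put the effect at 1/22 = 4.5 percentage points per record. The SAP states no counting rule for medications, a second record of the same drug in one participant need add nothing, and 22 is the planned number rather than the final denominator.

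Fourth, a false concomitant entry for memantine need not become a protocol deviation. SAP 13.4 has deviations identified during the study and categorized by study-team review; nothing says that they are derived from imputed dates.

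Finally, the opening words of the Appendix C note might be stretched to cover medications. Its place under the adverse-event table, and the allocation of appendices in SAP 13.1, do not support that.

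**Conclusion.** The point holds as a conflict between written rules. Two of the five start-date rows in Appendix B can place the start of a drug after its recorded stop and on the dosing day. The record then meets the first limb of the concomitant definition and the ended-before-IP condition for prior medications, so it could appear in Table 14.1.4 although the drug is known to have ended before dosing. That goes beyond the protocol's default, and SAP 6.1 does not declare it as a change.

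Its size is small. The number of affected records is unknown and may be zero. Only descriptive medication tables and listings are touched; TEAE incidence and the secondary endpoints do not depend on these dates. The 10-day and 80-day examples rest on the assumed first-dose date, but the conflict itself does not. It is a minor point, worth correcting because the sponsor already has the repair in Appendix C.

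**What to change.** - Repeat under Appendix B the Appendix C note, in both directions: start after stop, and stop before start.
- State in SAP 13.8 that a medication with a complete stop date before the first dose is classified as prior, whatever its imputed start date.

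One drafting caution. The first half of the Appendix C note covers complete stop dates only. If the start is 2021 only and the stop is March 2021 with the day missing, Appendix B gives a stop of 31 March 2021 and, with the assumed first dose, a start of 20 May 2021. The mirror half of the note would then move the stop to 31 May 2021. Wording the tie-break to include stop dates whose known month or year already precedes dosing avoids this.

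The cost is a few sentences in the SAP and a small change to the date derivation. No new data are needed, and no other analysis changes.

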### 19.3 Appendix-C Adverse Event Start/Stop Date Imputation

Parameter	Missing	Additional Conditions	Imputation
Start date for AEs	D	M and Y same as M and Y of investigational product administration	Date of investigational product administration
		M and/or Y not same as date investigational product administration	First day of month
	D and M	Y same as Y of investigational product administration	Date of investigational product administration
		Y prior to Y of investigational product administration but same as Y of screening date	Date of screening date
	D, M, Y	None - date completely missing	Date of investigational product
Stop date for AEs	D	M and Y same as M and Y of investigational product administration	Date of investigational product administration
		M and/or Y not same as date of investigational product administration	Use last day of month
	D and M	Y same as Y of investigational product administration	Date of investigational product
		Y not same as Y of investigational product administration	Use Dec 31
	D, M, Y	None - date completely missing	No imputation, but assume ongoing

[figure not shown]
Note: In all cases, if an estimated start date is after a complete stop date, use the first day of the stop date month. Similarly, if the estimated stop date is before a complete or imputed start date, use the last day of the start day month.

[figure not shown]

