12.2. Adverse and Serious Adverse Events

12.2.1. Adverse Event Definition

An AE is any untoward medical occurrence in a patient or clinical investigation participant administered a pharmaceutical product and that does not necessarily have a causal relationship with this treatment. An AE can therefore be any unfavorable and unintended sign (including an abnormal laboratory finding), symptom or disease temporally associated with the use of a medicinal (investigational) product whether or not related to the medicinal (investigational) product. In clinical studies, an AE can include an undesirable medical condition occurring at any time, including baseline or washout periods, even if no study treatment has been administered.

A TEAE is defined as an adverse event with onset after the start of IP, or any worsening of a preexisting medical condition/adverse event with onset after the start of IP and throughout the study. The term IP includes any Sage IP, a comparator, or a placebo administered in a clinical study.

Laboratory abnormalities and changes from baseline in vital signs, and ECGs are considered AEs if they result in discontinuation or interruption of study treatment, require therapeutic medical intervention, meet protocol-specific criteria (if applicable) or if the investigator considers them to be clinically significant. Any abnormalities that meet the criteria for an SAE should be reported in an expedited manner. Laboratory abnormalities and changes from baseline in vital signs and ECGs that are clearly attributable to another AE do not require discrete reporting (eg, electrolyte disturbances in the context of dehydration, chemistry and hematologic disturbances in the context of sepsis).

All AEs that occur after any participant has signed the informed consent and throughout the duration of the study, whether or not they are related to the study, must be reported to Sage Therapeutics.

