#### 16.1 Adverse Events

TEAEs are defined as any AEs with an onset date on or after the date of the first dose of IP or any worsening of a preexisting medical condition/AE with onset after the start of IP and throughout the study. An AE leading to treatment discontinuation is defined as an AE with action taken of the investigational product as Drug Withdrawn. AEs will be coded using the Medical Dictionary for Regulatory Activities MedDRA version 23.1.

An overall summary of TEAEs, including the number of events, reported, the number and percentage of participants reporting at least one TEAE, the number and percentage of participants reporting at least one related TEAE, Number and percentage of participants by maximum severity, the number and percentage of participants discontinuing due to an adverse event, the number and percentage of participants with at least one serious adverse event, and the number and percentage of deaths will be presented.

A breakdown of the number and percentage of participants reporting each TEAEs, categorized by System Organ Class (SOC) and preferred term (PT), will be presented. Note that counting will be by a participant, not event, and participants are only counted once within each SOC and PT.

A further tabulation of these data, categorized by relationship (to SAGE-718), will be presented. Participants with multiple events within a particular body system or preferred term will be counted under the category of their drug-related event (related and not related) within SOC and PT. Relationship to SAGE-718 is categorized as related or not related.

A summary of events reported, categorized by severity, will also be provided. Participants with multiple events within a particular SOC and PT will be counted under the category of their most severe event in the following order: severe> moderate> mild within that SOC and PT.

A summary of adverse events leading to discontinuation of SAGE-718 will be provided, grouped by body system and preferred term.

All adverse events (including non-treatment-emergent events) recorded on the CRF will be listed.

Handling of missing AE start dates is defined in Appendix-C. Missing data for severity or relatedness to treatment will not be imputed.

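### SAP Appendix C can turn an adverse event recorded as over before dosing into a Day 1 TEAE, when its start month is missing and its stop date is partial

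*SAP*

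**What the plan says.** The rows and notes that matter are all in SAP 19.3 (Appendix C).

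- **Start, day and month missing.** If "Y same as Y of investigational product administration" holds, the start becomes the first-dose date. If instead "Y prior to Y of investigational product administration but same as Y of screening date" holds, it becomes the screening date.
- **Start wholly missing** ("None - date completely missing"). The start becomes the first-dose date.
- **Stop, day missing, month other than the dosing month.** The instruction is "Use last day of month".
- **Stop, only a year known, and not the dosing year.** The stop becomes 31 December of that year.
- **Note, sentence 1.** "if an estimated start date is after a complete stop date, use the first day of the stop date month".
- **Note, sentence 2.** "if the estimated stop date is before a complete or imputed start date, use the last day of the start day month".

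The note is stated to apply in all cases. SAP 13.1 and 16.1 send adverse-event date handling to this appendix. SAP 16.1 then classifies: "TEAEs are defined as any AEs with an onset date on or after the date of the first dose of IP", or any worsening of an existing condition after the start of drug. Protocol 12.2.1 is worded differently: "A TEAE is defined as an adverse event with onset after the start of IP". SAP 13.1 and Protocol 13.6.1 likewise require onset after the first dose.

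**The concern.** The two sentences of the note treat the same evidence in opposite ways. A complete stop date before dosing overrides a guessed Day 1 start. A partial stop date whose known month is also before dosing does not: the guess stands and the recorded month is overwritten. Losing only the day of the stop date reverses the classification.

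TEAE incidence is the sole primary endpoint. Adverse events are collected from consent (Protocol 12.2.1), and screening assessments begin at Day -21, so an event can end in the calendar month before dosing. Under SAP 16.1 the error can only raise the incidence. It also adds an entry to the system organ class, severity and relatedness tables, and gives the event a derived duration that runs to the end of the dosing month.

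**Working it through.** **Denominator.** The SAP wants 20 completers at 10% dropout: 20 / (1 − 0.10) = 22.2, in line with its figure of approximately 22. This number only scales the impact.

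**Literal application of Appendix C.** The dates are my test assumptions. Cases A to D and G: first dose 10-Jun-2021, screening 24-May-2021. Cases E and F: first dose 08-Jan-2021, screening 20-Dec-2020. A month and year alone means that the day is missing.

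| Case | Recorded start | Recorded stop | Start / stop from the table rows | Start / stop after the note | TEAE under SAP 16.1 |
|---|---|---|---|---|---|
| A | 2021 only | May 2021 | 10-Jun / 31-May | 10-Jun / 30-Jun | Yes |
| B | missing | May 2021 | 10-Jun / 31-May | 10-Jun / 30-Jun | Yes |
| C | 2021 only | 28-May-2021 | 10-Jun / 28-May | 01-May / 28-May | No |
| D | May 2021 | May 2021 | 01-May / 31-May | unchanged | No |
| E | 2020 only | Dec 2020 | 20-Dec-2020 / 31-Dec-2020 | unchanged | No |
| F | missing | Dec 2020 | 08-Jan-2021 / 31-Dec-2020 | 08-Jan-2021 / 31-Jan-2021 | Yes |
| G | 15-Jun-2021 | Jun 2021 | 15-Jun / 10-Jun | 15-Jun / 30-Jun | Yes |

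- A, B and F are wrong: the record puts the end of the event in a month before dosing. A stop recorded as 2020 only gives the same result as F, because its row also yields 31-Dec-2020.
- A and C differ only in the missing stop day. In C sentence 1 applies; in A it does not, because the stop is not complete.
- D and E show that a known start month, or a start year that is the screening year and before the dosing year, avoids the problem.
- G shows why sentence 2 exists. A missing stop day in the dosing month is imputed to the first-dose date, which can precede a real later onset. That use is sound.

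**Impact per case.** A participant with no other TEAE who enters the numerator this way adds 1/22 = 4.5 percentage points, or 1/20 = 5.0 if 20 are dosed. A participant who already has another TEAE adds nothing to the overall incidence, but may still add an entry by system organ class and preferred term.

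**The case against.** **The record should hardly ever occur.** The schedule places consent in the Day -21 to Day -8 column. A 21-day span is shorter than any calendar month, so it touches at most two. If an event that began after consent ended in the month before dosing, it must also have begun in that month. A site could then enter the start month, and the event would be handled as in case D. Protocol 12.2.4 requires onset and resolution dates and times, there are several visits before dosing, and monitors verify source data. This stands as to frequency. It does not remove the case: Protocol 7.1.1 ties only the assessments after consent to Day -21, so earlier consent is possible, and a start field can still be left blank when events are reported from memory by participants with cognitive impairment.

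**Defaulting to treatment-emergent is the cautious choice.** That is right where timing is unknown. Here the stop month settles it, and sentence 1 already accepts that reasoning for complete stop dates.

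**The TEAE result depends on the definition.** This stands. Only SAP 16.1 makes a start dated on the first-dose day a TEAE outright. Under SAP 13.1, Protocol 13.6.1 and Protocol 12.2.1, a date without a time that equals the first-dose date does not settle the matter. A reader might infer that every such record is misclassified whichever definition is used; the documents do not support that.

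**A reader might also infer a general inflation of the primary endpoint**, for instance from the share of pre-dose days that fall in an earlier calendar month. That share says nothing about how often the start month and part of the stop date are missing together, so it does not measure the risk.

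**Conclusion.** The rule is wrong as written, within narrow limits. It misfires when three things hold together: the start is wholly missing, or only its year is known and equals the dosing year; the stop is partial; and the known part of the stop lies before the first-dose month or year. The event then keeps a guessed Day 1 onset and loses its recorded end month, and SAP 16.1 counts it as a TEAE. I found no other passage in either document that overrides this.

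The size is 4.5 points of incidence for each affected participant with no other TEAE, assuming 22 in the Safety Set. The number of such participants cannot be known from the documents and is probably very small. This is a minor correction to the primary-endpoint derivation, and no reason to expect a materially biased result.

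**What to change.** Extend sentence 1 of the Appendix C note to partial stop dates and narrow sentence 2, for example:

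> If the start month is unknown and the known parts of a complete or partial stop date show that the AE ended before the date of first dose, impute the start as the first day of the stop month (1 January of the stop year if only the year is known), or as the screening date if that falls later within the same stop month or year and not after a complete stop date. Do not classify the AE as treatment-emergent. Move an imputed stop date forward only when the start date is complete, or when its known month and year are later than the imputed stop.

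Keep the present sentence 1 for records with a known start month and a complete stop date. Query a record whose known start year is later than its stop year, because it contradicts itself.

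With this text, cases A and B become 24-May to 31-May-2021 and case F becomes 20-Dec to 31-Dec-2020, none of them TEAEs. Case C stays a non-TEAE, and D, E and G do not change. Confining the screening date to the stop month or year, and to no later than a complete stop, prevents a new start-after-stop conflict. Events of truly ambiguous timing still default to TEAE.

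The two TEAE wordings in the SAP (13.1 and 16.1) should be aligned at the same time, so that the status of a Day 1 imputed start is defined.

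The cost is a few sentences, a small derivation change and test records such as those above. No new data are needed. If the database is already locked, SAP 6.0 provides for describing and justifying the change in the study report.
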